Do Combined Oral Contraceptives Protect Against Anterior Cruciate Ligament Injuries in Female Athletes?

April 28, 2025

[name] MD¹, [name], MA², [name] PhD¹

¹ Kerlan Jobe Orthopedic Institute

² Cedars-Sinai Department of Obstetrics and Gynecology

TABLE OF CONTENTS

PROTOCOL SUMMARY	3
GENERAL INFORMATION	3
1.0 BACKGROUND, RATIONALE	4
2.0 STUDY OBJECTIVES	4
3.0 STUDY POPULATION	5
3.1 Selection of the Study Population	5
3.2 Inclusion Criteria	5
3.3 Exclusion Criteria	5
3.4 Subject Recruitment	5
3.5 Subject Screening and Enrollment	5
4.0 STUDY DESIGN AND METHODS	6
5.0 DATA COLLECTION AND MANAGEMENT	7
5.1 Data Procurement	8
5.2 Variables Collected	8
5.3 Source Documents	8
5.4 Data Collection and Storage	8
5.5 Confidentiality and Security of Data	8
6.0 DATA AND SAFETY MONITORING	8
6.1 Data and Safety Monitoring Plan	9
6.2 Quality Control and Quality Assurance	9
7.0 STATISTICAL CONSIDERATIONS	9
7.1 Study Outcome Measures	9
7.1 Sample Size Considerations	10
8.0 REFERENCES	10

PROTOCOL SUMMARY

Purpose and Knowledge to be Gained	
 The purpose of this study is to investigate the impact of combined oral contraceptive (COC) use on serum relaxin levels, ACL laxity, and rate of ligamentous injury among collegiate female athletes Previous research suggests COC use may decrease serum relaxin levels, which could decrease ACL laxity and potentially protect against ACL injury (which is disproportionately higher in female athletes vs male athletes)
Research Procedures	
 Assessment of baseline contraceptive status and initiation of study COC if participant desires Participants will undergo the following assessments at baseline and at the four-month time point 
 (1) Serum relaxin level (2) Knee joint anterior and posterior laxity will be tested using a KT-2000 arthrometer (Medmetric Corp, San Diego, CA) (3) Motion Tracking Analysis (4) Reported knee injury during study time period
Subject Population	
 150 female collegiate athletes competing in sports considered high-risk for ACL tears (basketball, soccer, and volleyball) Recruited from surrounding universities (Loyola Marymount, Pepperdine) where Cedars-Sinai Kerlan Jobe-affiliated orthopedic surgeons practice Participants who want to remain on no hormonal contraception or want to take study COC
Duration	
 The study includes 2 in-person visits and one phone follow-up. The total study duration is 12 months

GENERAL INFORMATION

CSMC Co-Investigators	[name] MD, [name] PhD
Sponsor/Funder	Internal Funding
Collaborating Institutions Involved in the Research	None

1.0 BACKGROUND, RATIONALE

Increased female athletic participation was set forth after the establishment of Title IX.¹¹ With this increase in activity came a dramatic rise in ACL injuries, revealing a significant gender disparity with women having a 2-to-10 times greater risk of ACL rupture.⁹ While numerous studies have revealed anatomic, neuromuscular and hormonal differences play a role,^{3, 6, 7} one question that has not fully been addressed is the possible protective role of combined oral contraceptives (COCs).

Prevalence of COC use among female athletes has been estimated at 40% to 50%, showing a significant acceptance of COC use by many female athletes.^{2, 12} Previous literature suggests that fluctuating hormones not only play a role in weakening the structure of the female ACL but also increase knee joint laxity, leading to poorer lower extremity biomechanics during sports and activities.^{5, 6} While some risk factors are not modifiable, such as the size of a woman's ACL or femoral notch, the ability to safely alter a female's hormonal profile to confer a more protective, favorable environment may theoretically provide a viable intervention for the female athletic community in ACL injury prevention as well as in post-ACL reconstruction rehabilitation.

Thus, advancing our knowledge of the underlying pathophysiological mechanisms of ACL injuries will further the development of prevention, rehabilitation and training strategies to reduce the risk of sport-related injury, thereby enhancing the beneficial effects of physical activity on women's health for all ages. With 4 out of 5 heterosexually active women in the U.S. using COC in their lifetime, this research may also contribute to growing evidence of non-contraceptive benefits of COCs.

2.0 STUDY OBJECTIVES

We plan to investigate the hypothesis that combined oral contraceptives (COCs) reduce serum relaxin levels and ligament laxity in collegiate female athletes. Though this study cannot prove causality, we will also observe if rate of ligamentous injury in female athletes is reduced among women taking COC. Our specific aims are as follows:

Aim 1: To evaluate relaxin levels in female athletes on COC or no hormonal contraceptive

Aim 2: To quantify anterior and coronal plane (varus/valgus) knee laxity between female athletes using combined oral contraceptives and those who are not using any hormonal treatment.

Aim 3: To track the rate of ACL and other ligamentous injuries (ruptures / sprains) among female athletes and determine if COCs have a protective effect.

3.0 STUDY POPULATION

3.1 Selection of the Study Population

- We aim to recruit a convenience sample of 150 female collegiate athletes competing in sports considered high-risk for ACL tears (basketball, soccer, and volleyball)
- Participants will be from surrounding universities (Loyola Marymount, Pepperdine)
- These female collegiate athletes will be English-speaking, so there is no need for non-English speaker consent considerations. If, however, a subject wishes to discuss anything in another language, CSMC interpreter services will be requested.

3.2 Inclusion Criteria

- Female
- 18 years of age or older
- Currently playing basketball, soccer, or volleyball at Loyola Marymount or Pepperdine
- If not currently on COC, regular menstrual cycle occurring every 21-35 days

3.3 Exclusion Criteria

- Previous ACL injury (Previous ACL injury, on the same knee or the contralateral knee, places you at a significantly increased risk of subsequent ACL rupture which would provide a confounding effect in our study. Subsequent treatment of that ACL injury, whether with surgery or non-operative management, would also affect subsequent ACL injury risk.)
- Underlying neuromuscular disease
- For COC use group only: Medical contraindication to COC use
- History of pregnancy (Excluding previous pregnancies eliminates a potential confounder --- women may have lasting changes from carrying a pregnancy in the past.)
- Desire to conceive in the next year

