3.5 Subject Screening and Enrollment

All female athletes for basketball, soccer and volleyball will be provided an informational flyer about our study and be given the opportunity to approach [name] via in-person meeting, telephone or email. Potential subjects who are interested will be consented for the study after discussion of the study and continued interest in participation. They will then be asked to complete a screening questionnaire evaluating medical, surgical, reproductive, and injury history. This screening questionnaire will be returned via email to the study coordinator.

Those meeting above enrollment criteria will continue participation and onboarded for the study by the study coordinator.

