- Participants will be kinematically evaluated using a portable, non-invasive, 3-dimensional motion capture system (Awinda, Xsens Technologies, The Netherlands).
- Each athlete will be asked to perform a singled-legged drop while the motion tracking system collects and records trunk flexion angle (degrees), hip adduction (degrees), and internal/external and coronal plane rotation (both in degrees) of the knee.
- Data will be collected and averaged over three trials at each of the two time points – baseline and 4th month of study participation.

Interval Injury Assessment (Aim 3):

- Ligamentous injury will be monitored over the entire length of the study, tracking the date, location, and mechanism of injury for each event by participant report. Follow-ups to ask about any injury will occur weekly at each training room session, or sooner if we are contacted by athlete or trainer for a more significant injury that needs to be seen urgently in the office by team physician.

Medical History Review:

- Medical history will be queried for the data points in section 5.2 at the screening visit and at Visit #1.

Schedule of Procedures

All procedures are research related

Procedures	Screening Visit	Visit #1 (4-month visit)	Phone follow-up (One year)
Medical History	X	X	
Prescribing contraception*			
Blood draw (Serum relaxin level)	X	X	
Joint Laxity Testing	X	X	
Motion Tracking analysis	X	X	
Obtain interval medical history		X	X

*Only for those who want to be put on study contraception.

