7.0 STATISTICAL CONSIDERATIONS

7.1 Study Outcome Measures

- **Data Analysis:** Statistical analysis will be performed using SAS statistical software (SAS Institute Inc., Cary, NC, USA) with significance set at $p<0.05$. Differences in the two timepoints will be evaluated between the two groups. Multiple regression will be used to analyze rate of injury as a function of OC use (group), joint laxity, motion analysis, and serum relaxin, and additional demographic data. Post-hoc ANOVA, or non-parametric alternative, will be used to evaluate continuous variables (joint laxity, motion analysis, and serum relaxin levels) between groups.
- Serum relaxin-2 level will be measured using a Quantikine Human Relaxin-2 Immunoassay (DRL200). All samples will be run in duplicate and relaxin-2 concentrations will be calculated from the standard curve. The intra-assay and inter-assay coefficients of variation and minimum detection limit will be determined and reported.
- Joint laxity measurements will be evaluated using the KT-2000 and the Beighton Score. The KT-2000 measures anterior and posterior displacement (mm) of the tibia relative to the femur when an anterior and posterior load are applied to the tibia. The amount of tibial displacement provides information on ACL laxity. The Beighton score is screening technique for measuring generalized joint hypermobility.¹ It requires the performance of 5 maneuvers, four passive bilateral and one active unilateral performance:
 1. Passive dorsiflexion and hyperextension of the fifth MCP joint beyond 90°
 2. Passive apposition of the thumb to the flexor aspect of the forearm
 3. Passive hyperextension of the elbow beyond 10°
 4. Passive hyperextension of the knee beyond 10°
 5. Active forward flexion of the trunk with the knees fully extended so that the palms of the hands rest flat on the floor

The Beighton score is based on a 9-point scale with ≥ 4 considered hypermobile.

- Continuous measures of trunk flexion, hip adduction, and internal/external and coronal plane rotation of the knee measured during a singled-legged drop using the motion tracking equipment mentioned above in section 4.0 (Aim 2). These outcomes measures are all in angles (degrees). Increased valgus knee motion (in the coronal plane) and landing with the femur in adduction and internal rotation has been suggested to predispose athletes to injury when landing from a jump.¹⁰

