7.1 Sample Size Considerations

The primary outcome measure of this study is the rate of ligament injury. Therefore, our sample size requirements were based on this measure. Previous research indicates female athletes' risk of injury is sport dependent. In Dragoo et al.'s 2011 analysis, they report a 60% rate of ACL injury among basketball players, and a ~30% injury rate among soccer, gymnastics, and lacrosse female athletes.⁴ Whereas field hockey and volleyball had a reported 0% rate of injury. Thus, we believe it is reasonable to estimate that females not taking oral contraceptives will have an estimated 30% risk of ligament injury, which we aim to demonstrate a 20% absolute reduction to 10% risk of injury among females taking OCs. Assuming equal sizing, based on previous studies that demonstrate approximately half of female athletes are on OCs,² we estimate a total sample size of 140 will provide approximately 80% power to detect an ACL Injury rate difference of 10% (OC) versus 30% (non-OC).

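### Only previous ACL injury is excluded, but the outcome counts all ligament injuries; the injury model should carry previous non-ACL ligament injury as one baseline covariate

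*Combined protocol and SAP*

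**What the plan says.** **Eligibility.** Section 3.3 excludes "Previous ACL injury, on the same knee or the contralateral knee", and gives as the reason that such an injury "places you at a significantly increased risk of subsequent ACL rupture which would provide a confounding effect in our study". The remaining exclusions concern neuromuscular disease, contraindication to COCs, pregnancy history and plans to conceive. None concerns earlier injury to another ligament.

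**Outcome.** Aim 3 in section 2.0 is "To track the rate of ACL and other ligamentous injuries (ruptures / sprains) among female athletes". Section 7.1 (Sample Size Considerations) states: "The primary outcome measure of this study is the rate of ligament injury". Section 4.0 adds: "Ligamentous injury will be monitored over the entire length of the study, tracking the date, location, and mechanism of injury".

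**Groups.** Under section 4.0 women enter by their own contraceptive preference. There is no randomization.

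**Data.** Under section 3.5 candidates "complete a screening questionnaire evaluating medical, surgical, reproductive, and injury history". Section 5.2 lists medical, surgical and menstrual/gynecologic history. Injury history is not a separate item there.

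**Model.** Section 7.1 (Study Outcome Measures): "Multiple regression will be used to analyze rate of injury as a function of OC use (group), joint laxity, motion analysis, and serum relaxin". The sentence then adds demographic variables without naming them.

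**The concern.** The plan treats previous ACL injury as a confounder and removes it by exclusion. That step covers only the ACL, while the outcome covers every ligament. A woman with an earlier medial collateral or ankle ligament injury can enrol, and a new sprain counts as an event.

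With self-selected groups, nothing in the design balances such a history between COC users and non-users. Adjustment would have to come from the regression, and no term there represents previous injury. Injury history is not demographic data in the usual sense. Laxity, landing kinematics and relaxin are current measurements, not records of past injury.

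At stake is the COC effect on the declared primary outcome. If earlier injury predicts later injury and its share differs between groups, part of the estimated effect belongs to injury history.

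**Working it through.** **1. The plan's own figure.** Inputs from 7.1 (Sample Size Considerations): 30% v 10%, equal groups, about 80% power, total 140. Alpha is 0.05; two-sided is assumed.

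Per group without continuity correction: [1.96·√(2·0.2·0.8) + 0.842·√(0.3·0.7 + 0.1·0.9)]² / 0.2² = 61.6, so 62 (124 in total). With continuity correction it is 72 (144 in total). At 70 per group, power is 79.2% with the correction and 81.3% by Fisher's exact test. The stated 140 is therefore reproduced, and this point does not dispute it.

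**2. Expected events.** 70 × 0.30 + 70 × 0.10 = 21 + 7 = 28.

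**3. Bias if COCs have no effect.** Let previous non-ACL injury multiply risk by M, with prevalence p_u in users and p_n in non-users. The unadjusted risk ratio is then

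RR = [1 + p_u(M − 1)] / [1 + p_n(M − 1)].

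The documents give none of these three quantities; every value below is an assumption.

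| p_u v p_n | M = 1.5 | M = 2 | M = 3 |
|---|---|---|---|
| 25% v 40% | 1.125/1.20 = 0.94 | 1.25/1.40 = 0.89 | 1.50/1.80 = 0.83 |
| 30% v 50% | 1.15/1.25 = 0.92 | 1.30/1.50 = 0.87 | 1.60/2.00 = 0.80 |
| 50% v 30% (reversed) | 1.25/1.15 = 1.09 | 1.50/1.30 = 1.15 | 2.00/1.60 = 1.25 |
| equal | 1 | 1 | 1 |

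**4. Effect on the test.** Take 70 per group, 30% risk in non-users and risk r = 0.30 × RR in users, with no COC effect. With D = 0.30 − r, SE₀ = √[2p̄(1 − p̄)/70] and SE₁ = √{[0.21 + r(1 − r)]/70}, the two-sided 5% test rejects with probability Φ[(D − 1.96·SE₀)/SE₁] + Φ[(−D − 1.96·SE₀)/SE₁].

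Example, RR = 0.80: r = 0.24, D = 0.06, p̄ = 0.27, SE₀ = 0.0750, SE₁ = 0.0749, giving 12.5%.

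- 30% v 50%: 6.1%, 8.2% and 12.5% for M = 1.5, 2 and 3.
- 50% v 30% (reversed): 6.3%, 9.0% and 15.5%.
- A wider imbalance of 30% v 60%: ratios 0.88, 0.81 and 0.73, with rejection in 7.4%, 11.6% and 19.6%.

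**5. Comparison with the planned effect.** The planned ratio is 0.10/0.30 = 0.33. The formula cannot fall below 1/M. At M = 3 it reaches 0.33 only if no user and every non-user has the history.

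**6. Room in the model.** Suppose laxity enters as a single measure and the four motion angles of section 4.0 enter separately. The named terms are then group 1 + laxity 1 + motion 4 + relaxin 1 = 7, before any demographic variable. That is 28/7 = 4 events per term, or 28/8 = 3.5 with one more.

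**The case against.** Several objections have force.

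- **The reasoning in 3.3 is specific to the ACL.** A reader might infer that the protocol itself makes any previous ligament injury a confounder. It does not. It says that ACL injury raises the risk of later ACL rupture. That an old sprain predicts later ligament injury is an added premise.
- **No link with COC use is shown.** Confounding needs one, and no section suggests that past sprains influence contraceptive choice. Self-selection makes imbalance possible; it does not establish it.
- **The endpoint wording wavers.** The sample-size text quotes ACL rates and ends on an ACL injury difference. If the endpoint were ACL injury alone, the exclusion would largely match it. The declared primary outcome, Aim 3 and the monitoring text nevertheless cover all ligaments. A reader might go further and assume that most counted events will be non-ACL; the documents give no split.
- **The item may already be recorded.** A reader might conclude from 5.2 that injury history is lost. Medical history is listed there and could hold it. What stands is that it is not a named item and not in the model.
- **Laxity may absorb part of the effect** of an earlier knee injury. It is not shown to do so, and knee displacement says nothing of an ankle.
- **Other covariates compete.** The sample-size section itself calls injury risk sport dependent, yet sport is not named in the model either. That omission has firmer support in the documents.

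Section 2.0 concedes that the study cannot prove causality. That tempers the claim but does not justify leaving a requested baseline variable unused.

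**Conclusion.** The point holds in a limited form. The ACL-only exclusion does not reach the full declared outcome, the groups are self-selected, and the injury model as written leaves previous non-ACL ligament injury uncontrolled although the history is requested at screening.

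Whether this biases the result rests on two unverified conditions: that such a history predicts later injury, and that its prevalence differs between groups. If either fails, the bias is zero. Under the main assumed figures the spurious ratio is 0.80 to 0.94, and it exceeds 1 if the imbalance reverses.

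A reader might infer that this could explain an effect of the planned size. Step 5 shows that, for multipliers up to 3, it could not short of total separation of the groups. It would matter more if the true effect were much smaller than planned. The change is worth making, but the study does not stand or fall by it.

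**What to change.** In section 5.2, list previous ligament injury other than ACL as a yes/no item taken from the screening questionnaire, with the joint recorded for description only. In section 7.1 (Study Outcome Measures), prespecify the yes/no item as a single binary baseline covariate in the injury model. Do this before outcome data are analysed, since adding it later would be a post hoc choice. Keep the ACL exclusion as it is.

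The questionnaire is not reproduced in the documents, so check that it identifies ligament and joint; if not, one question must be added.

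The cost is small but not nil: one more term against about 28 expected events. The other covariates should therefore be named and kept few, and the joint should not be modelled. No gain in precision is claimed: if the injury model is logistic, adjustment generally does not reduce the standard error of the log odds ratio. The reason for the term is control of possible confounding.

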3.4 Subject Recruitment

Female athletes will be recruited via two pathways:

- (1) Approached by [name], who along with other Cedar Sinai Kerlan-Jobe doctors, serve as the team physician for the schools.
- (2) Self-referral via recruitment materials posted in training facility

3.5 Subject Screening and Enrollment

All female athletes for basketball, soccer and volleyball will be provided an informational flyer about our study and be given the opportunity to approach [name] via in-person meeting, telephone or email. Potential subjects who are interested will be consented for the study after discussion of the study and continued interest in participation. They will then be asked to complete a screening questionnaire evaluating medical, surgical, reproductive, and injury history. This screening questionnaire will be returned via email to the study coordinator.

Those meeting above enrollment criteria will continue participation and onboarded for the study by the study coordinator.

4.0 STUDY DESIGN AND METHODS

Data will be collected prospectively throughout participant intake and study progression. Given the personal nature of women's contraceptive preferences, we will enroll three categories of female athletes:

- (1) Women who are not on hormonal contraception and have no plan to start in the next year
- (2) Women who are not on hormonal contraception and would like to initiate study COC
- (3) Women who are currently on hormonal contraception and would like to switch to study COC

For those participants who would like to start study COC, women will be prescribed a daily oral contraceptive containing ethinyl estradiol 20mcg/norethindrone 1mg.

Women will maintain a contraceptive compliance diary via paper or Word document which they can submit to us in person or electronically. Orthopedic testing will start during the fourth menstrual/COC cycle due to delay in COC effect and theoretical cumulative protective effect of COC use. All three groups will undergo below testing to evaluate primary and secondary aims.

Serum Relaxin (Aim 1):

- Participants will have about 2ccs of blood drawn to measure serum relaxin levels at two time points:
 1. Baseline
 2. Fourth month of study participation - menstrual cycle-specific timing:
 - Participants not on COC:
 - Luteal phase of their menstrual cycle (Days 14-28)
 - This is when peak relaxin levels are noted to occur
 - Participants on COC:
 - Pill pack days 14-28
 - Women on COC have suppressed ovulation and thus no true luteal phase, but will undergo testing during the same time period

Joint Laxity (Aim 2):

- Joint laxity will be tested at two separate time points:
 1. Baseline
 2. Fourth month of study participation – synced with serum collection for relaxin level testing.
- Joint Testing:
 - Each participant's bilateral knee joint laxity will be tested using a KT-2000 arthrometer (Medmetric Corp, San Diego, CA) for anterior and posterior laxity.
 - Laxity and biomechanical testing will be done in the athletes' training room on campus.
 - To eliminate inter-rater differences in the laxity measurement, only one examiner will conduct all knee laxity measurements.

- With a passive anterior and posterior drawer test at 67N and 87N, an average displacement (mm) for three cycles will be determined.
- A Brighton score will be calculated with goniometer by a one examiner to assess generalized hypermobility at each time point.

Motion Tracking Analysis (Aim 2):

- Participants will be kinematically evaluated using a portable, non-invasive, 3-dimensional motion capture system (Awinda, Xsens Technologies, The Netherlands).
- Each athlete will be asked to perform a singled-legged drop while the motion tracking system collects and records trunk flexion angle (degrees), hip adduction (degrees), and internal/external and coronal plane rotation (both in degrees) of the knee.
- Data will be collected and averaged over three trials at each of the two time points – baseline and 4th month of study participation.

Interval Injury Assessment (Aim 3):

- Ligamentous injury will be monitored over the entire length of the study, tracking the date, location, and mechanism of injury for each event by participant report. Follow-ups to ask about any injury will occur weekly at each training room session, or sooner if we are contacted by athlete or trainer for a more significant injury that needs to be seen urgently in the office by team physician.

Medical History Review:

- Medical history will be queried for the data points in section 5.2 at the screening visit and at Visit #1.

Schedule of Procedures

All procedures are research related

Procedures	Screening Visit	Visit #1 (4-month visit)	Phone follow-up (One year)
Medical History	X	X	
Prescribing contraception*			
Blood draw (Serum relaxin level)	X	X	
Joint Laxity Testing	X	X	
Motion Tracking analysis	X	X	
Obtain interval medical history		X	X

*Only for those who want to be put on study contraception.

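### Switchers already on hormonal contraception at baseline appear to be pooled with new starters in the change analysis; a smaller fault is that Days 14-28 is not the luteal phase in longer cycles

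*Combined protocol and SAP*

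**What the plan says.** **Groups.** Section 4.0 lists three categories: (1) women not on hormonal contraception with no plan to start, (2) women not on it who want to start the study COC, and (3) "Women who are currently on hormonal contraception and would like to switch to study COC". It adds: "All three groups will undergo below testing to evaluate primary and secondary aims". No washout is described for category 3. In 7.1 Study Outcome Measures, differences between the two timepoints are compared across two groups, with a between-group ANOVA or non-parametric alternative for laxity, motion and relaxin. The timepoint of that ANOVA is not given, nor is the handling of category 3.

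**Month-4 timing.** The blood draw is described as "Fourth month of study participation - menstrual cycle-specific timing". For women not on COC it is "Luteal phase of their menstrual cycle (Days 14-28"), because relaxin is said to peak then. For COC users it is pill pack days 14-28. Laxity testing at month 4 is "synced with serum collection for relaxin level testing". Section 3.2 requires: "If not currently on COC, regular menstrual cycle occurring every 21-35 days".

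**Baseline timing.** The baseline items for blood and laxity in Section 4.0 carry no cycle timing; the Schedule of Procedures only places them at the screening visit. Section 4.0 also says: "Medical history will be queried for the data points in section 5.2 at the screening visit and at Visit #1". Section 5.2 lists menstrual history but does not itemise cycle day at testing.

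**Wording conflict.** Section 4.0 says "Orthopedic testing will start during the fourth menstrual/COC cycle", yet lists a laxity test at baseline.

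**The concern.** Lower relaxin and laxity on COC is the hypothesis in Section 2.0. A woman already on hormonal contraception at baseline has had some or all of the effect before the first measurement, so her change score cannot show it fully. Mixing such women with new starters gives an estimate that depends on the recruitment mix. That mix could lean towards switchers: 7.1 Sample Size Considerations justifies equal groups by about half of female athletes already using OCs.

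Separately, Section 4.0 treats cycle phase as important enough to fix at month 4, but does so with calendar days that suit a cycle of about 28 days, and leaves phase free at baseline.

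Relaxin, laxity and motion measurements are also covariates in the injury regression in 7.1 Study Outcome Measures, so Aim 3 is touched as well as Aims 1 and 2.

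**Working it through.** **The plan's own figure.** The only computed figure is N = 140 for 10% versus 30% injury. At 70 per group, two-sided 5%, power is 0.85 (pooled normal), 0.81 (Fisher exact) or 0.79 (continuity-corrected). The stated power of about 80% is reproduced, and nothing below bears on it.

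**Assumptions not in the documents.** The luteal phase is the last P days of the cycle, P = 14 (range 12-16). Draws are spread evenly over the in-cycle window days, and the baseline day is random within the cycle. Mean levels are 0 (non-luteal), D (luteal) and S (on COC). D, w and the distribution of cycle lengths are not given.

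**1. Pooling.** Let f be the luteal share of the month-4 window and p = P/L the chance that a random baseline day is luteal (L is cycle length).
- Change in non-users: (f - p)D
- Change in starters: S - pD
- Change in switchers already at S: 0
- Starters minus non-users: S - fD, which equals the month-4 contrast; p cancels
- Switchers minus non-users: -(f - p)D, although nothing changed in the switchers

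Take S = 0 and L = 28, so f = 14/15 = 0.933 and p = 14/28 = 0.5. The pooled contrast is -(f - wp)D:

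| w | untimed baseline | phase-matched baseline, -(1 - w)fD |
|---|---|---|
| 0 | -0.93D | -0.93D |
| 0.25 | -0.81D | -0.70D |
| 0.5 | -0.68D | -0.47D |
| 0.75 | -0.56D | -0.23D |

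At w = 0.5 the untimed figure keeps 0.683/0.933 = 73%, and the phase-matched figure keeps 50%. The untimed figure is larger only because non-users drift with phase, adding a spurious 0.933 - 0.5 = 0.43D to the switcher comparison. If earlier methods give only half the suppression, the phase-matched share kept is 1 - 0.5w, or 75% at w = 0.5.

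**2. Does dropping switchers cost precision?** Take 75 non-users and 75 COC users (150 split equally), w = 0.5, and equal SD of change. The standard error in SD units is √(1/75 + 1/75) = 0.163 pooled and √(1/75 + 1/37.5) = 0.200 for starters only. Effect over standard error, per unit of effect in SDs:
- Phase-matched, full effect set to 1: 0.5/0.163 = 3.1 pooled; 1/0.200 = 5.0 starters only
- Untimed, in units of D: 0.683/0.163 = 4.2 pooled; 0.933/0.200 = 4.7 starters only

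The smaller comparison is the more informative one in both cases.

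**3. Month-4 window.** Days 14-28 are 15 days. Luteal share:

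| Cycle length | P = 14 | P = 12 to 16 |
|---|---|---|
| 28 | 14/15 = 93% | 80-100% |
| 30 | 12/15 = 80% | 67-93% |
| 31 | 11/15 = 73% | 60-87% |
| 35 | 7/15 = 47% | 33-60% |

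At P = 14 the mean over 31-35 days is (11 + 10 + 9 + 8 + 7)/75 = 60%. If a share q of non-users has such cycles and the rest are near 28 days, F = (1 - q) × 0.933 + q × 0.60. This gives 0.900, 0.867 and 0.833 for q = 0.1, 0.2 and 0.3. With S = 0 the month-4 contrast is proportional to F, so it is 96%, 93% and 89% of its 28-day value.

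**4. Untimed baseline.** Its phase variance is p(1 - p)D². The month-4 window itself carries f(1 - f)D², so the net addition over a baseline timed to that window is 0.25 - 0.06 = 0.19D² at 28 days, 0.25 - 0.20 = 0.05D² at 31 and 0.24 - 0.25 = -0.01D² at 35.

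**5. A count-back window.** The last 12 days before menses are all luteal for P = 12 to 16. If menses comes 3 days late, 9/12, 11/12 or 12/12 of the window is luteal (P = 12, 14, 16); if 3 days early, 9/12.

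**The case against.** Pooling is inferred: the plan never says that starters and switchers are combined. Aim 2 in Section 2.0 is framed as users versus non-users, and a month-4 ANOVA between them would fit the text. This stands as far as it goes, but the change comparison is also planned, names two groups where Section 4.0 has three, and gives no rule for category 3.

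On the window, luteal phase may be the instruction and the day range only a gloss. Then little is lost, but the two still conflict for long cycles and no way of locating the phase is given. The loss is modest in any case and rests on an assumed share of long cycles.

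Some stronger readings are tempting and should be resisted:
- **That the untimed baseline biases starters versus non-users, so an unadjusted month-4 contrast should become the main analysis.** The baseline term cancels on average if baseline cycle day is unrelated to group. The groups are self-selected, and a month-4 contrast alone does not remove pre-existing differences.
- **That short cycles misfit as badly.** In cycles of 21-27 days the window days that exist are luteal or nearly so; the remaining days fall after the cycle ends.
- **That there is no baseline laxity test.** The Protocol Summary, Section 4.0 and the Schedule of Procedures all place one at baseline, so the fourth-cycle sentence is a wording point.

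**Conclusion.** The concern holds, with prior exposure in category 3 as its main part. This is a matter of group definition, not of timing. If switchers are already at the on-COC level, a pooled, phase-matched change keeps 1-w of the effect: 75%, 50% and 25% at w = 0.25, 0.5 and 0.75. With an untimed baseline, 28-day cycles, a 14-day luteal phase and the on-COC level equal to the non-luteal level, it is -0.68D at w = 0.5 against -0.93D. Phase-matching baseline while the groups stay pooled moves the estimate further from the month-4 contrast.

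The month-4 window is a smaller point: about 4-11% of the contrast is lost if 10-30% of non-users have 31-35 day cycles. The untimed baseline mainly adds noise.

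A reader might infer that only Aims 1 and 2 are affected. The documents do not support that, because the same measurements enter the injury regression. Nor do they support the opposite inference that the sample size is wrong: it rests on injury rates alone. Confidence is medium, since w, D, luteal length and the share of long cycles all have to be assumed.

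**What to change.** 1. For relaxin, laxity and motion outcomes, base the change-from-baseline comparison on category 2 versus category 1 and report category 3 separately. State the timepoint of the ANOVA, and label any month-4 comparison that includes category 3 as users versus non-users. Keep the starters-versus-non-users change; do not replace it with an unadjusted month-4 contrast. *Cost:* fewer women in each COC comparison, though step 2 of the working shows a net gain at w = 0.5.
2. For women not on hormonal contraception, set the month-4 window by counting back from each woman's expected next menses, for example the last 12 days. *Cost:* individual scheduling around the single laxity examiner, for about 75 women if 150 split equally.
3. Record cycle or pill day at both test visits. Use the same window at baseline where scheduling allows, or adjust for recorded phase. *Cost:* a few date fields, and a wait of up to about one cycle where baseline is timed.
4. Say how category 3 and measurement phase are handled in the injury regression.
5. Reconcile the fourth-cycle sentence in Section 4.0 with the baseline laxity test.

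None of this needs an extra visit or assay.
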